Thus, the hypothesis of the current proposal is that the addition of spironolactone (50 mg/d) to selective ET_A inhibition (standard therapy) with ambrisentan (5-10 mg/d) is more effective than standard therapy alone at improving cardiopulmonary fitness and quality of life in patients with PAH.

Recent clinical trial data indicates that the initiation of combination therapy for treatment naïve PAH patients with ambrisentan and phosphodiesterase type-V inhibitors (PDE-Vi) (e.g., sildenafil/tadalafil) is superior to monotherapy alone for decreasing PAH-related clinical events. It is anticipated that this combination therapy will be incorporated into the expert consensus guidelines for the treatment and management of PAH patients. Importantly, aldosterone has been evaluated by our group in the context of soluble guanylyl cyclase-nitric oxide signaling, which, in turn, is the target of PDE-Vi therapies. In specific, we have demonstrated that aldosterone increases vascular oxidant stress levels to inhibit soluble guanylyl cyclase sensing by nitric oxide to diminish blood relaxation (Maron; Leopold). Therefore, it is anticipated that aldosterone inhibition with spironolactone will provide a synergistic mechanism with PDE-Vi by which to improve pulmonary vascular tone in patients with PAH.

II. Specific Aims

Specific Aim 1: Study the effect of combination ambrisentan (5-10 mg/d) + spironolactone (50 mg/d) on cardiopulmonary fitness as assessed by change from baseline (study drug day 1) at study drug day 90 for each of the two trial phases (See Section IV) on the following dimensions: (i) 6 minute walk distance and (ii) peak oxygen consumption (ml/kg/min)(pVO₂) at the completion of exercise.

Hypothesis: Improvements to pulmonary vascular remodeling and function mediated by selective ET_A inhibition plus aldosterone antagonism will influence favorably pulmonary vascular-right ventricular performance to enhance cardiopulmonary fitness and improve exercise tolerance.

Specific Aim 2: Study the effect of combination ambrisentan (5-10 mg/d) + spironolactone (50 mg/d) on cardiac output, right ventricular (RV) function, key biochemical measures of heart failure, and quality of life.

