A complete medical history, demographics, PAH history, and physical examination (PE) will be conducted during the Baseline Visit. Significant past or present illnesses, current prescription or nonprescription medications (including vitamins and herbal products), and history of allergies or idiosyncratic responses to drugs will be included. Any significant changes to the subject's medical condition, PE, and concomitant medications must be documented throughout the course of the study. A complete PE will be conducted at every clinic visit.

2. Vital Signs

Vital signs will be assessed at Baseline prior to starting study medication and then at every clinic visit. Vital signs include blood pressure, peripheral (radial/brachial artery) heart rate, respiration rate, and weight. Height will be collected at the Baseline visit.

Weight will be obtained at home every day during participation in the study. Subjects will be instructed to weigh themselves every morning and to maintain a diary of daily weights. Diary can be found in Appendix D.

3. Six Minute Walk Test

The intent of the 6MWT is to evaluate exercise capacity associated with carrying out activities of daily living. All 6MWTs will be conducted by qualified, trained personnel in a designated 6MWT area which meets the requirements as described in Appendix A. Prior to the start of each 6MWT the subject should rest (seated) for at least 5 minutes.

4. Borg Dyspnea Score

The Borg dyspnea score will be assessed following each 6MWT. The Borg dyspnea score is a 10-point scale rating the maximum level of dyspnea experienced during the 6MWT (Appendix A). Scores range from 0 (for the best condition) to 10 (for the worst condition).

5. WHO Functional Classification

The WHO functional classification for PAH (Appendix B) will be assessed at all Baseline prior to starting study drug and at all subsequent scheduled study visits.

6. Laboratory Testing

Clinical laboratory tests will be assessed at the Baseline visit prior to starting study drug. Clinical laboratory assessments will also be assessed at every clinic visit. Clinical laboratory testing is displayed in Appendix C.

Total amount of blood collected during the entire study is 120 mL.

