Study Secondary End-points: The secondary end-points are change from baseline (study drug day 1) at study drug day 90 for each of the two trial phases for cardiac output assessed noninvasively by the Innocor™ device¹¹, the minute ventilation/volume of expired carbon dioxide (V_E/VCO₂) slope at the completion of exercise as assessed by the Innocor™ step protocol; echocardiographically assessed RV geometry (RV dimensions, RV fractional area change, RV area and volume), pulmonary artery acceleration time, morphology of the pulmonary artery outflow tract Doppler envelope, and tricuspid annular plane systolic excursion (TAPSE) to assess RV function; and quality of life assessed by the SF-36 scale.

Innocor™ assessments and analysis of echocardiography and Innocor™ results will be performed at a single core facility (Brigham and Women's Hospital).

Additional Measures: Assessing volume status

Compared to other traditional diuretic pharmacotherapies, spironolactone induces a weak natriuretic effect to modulate subtle changes to circulating blood volume.⁴ However, in order to assess the potential effect of spironolactone on outcome in PAH due to diuresis rather than change in pulmonary vascular function, several clinical measures indicative of volume status will be assessed. These include, regular body weight measurement and jugular venous pressure monitoring assessed at 4-week intervals according to previously published methods,¹² as well as a record of all study participants' relevant cardiovascular medication (and doses) such as loop and thiazide diuretics. Tracking this information will allow for the study investigators to analyze outcome results according to diuretic status, and provide information regarding timing and extent to which spironolactone influences circulating plasma volume clinically.

Statistical Methods

A two-primary end-point study model will be used in the proposed trial, which is akin to previously published clinical trial reports in pulmonary arterial hypertension,¹⁰ as follows:

Physiological Measure of Performance: Peak VO₂

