Peak oxygen consumption (pVO₂) is a continuous response variable, and we will be comparing ΔpVO_2 from baseline to 90 days, and baseline to 180 days between control and intervention group. Difference in ΔpVO_2 , from baseline (day 1) to day 90, the treatment effect, will be compared using a 2-sided, paired Student's t test. There are few data on the distribution of change in VO₂ with interventions. Our prior studies, in patients with congenital heart defects, have shown that change in pVO₂ is normally distributed.¹¹ In our observational study of patients with congenital heart disease, those who engaged in frequent activity increased pVO₂ by 1.8 ± 3.2 mL/kg/min. This study included very heterogeneous diagnoses and levels of baseline pVO₂, and we anticipate the variance of the current study to be significantly lower. A true 1.0 mL/kg/min ΔpVO_2 difference would be clinically important. If the true difference in mean response of matched pairs is 1.0 ± 1.7 mL/kg/min, we will need 25 subjects to be able to reject the null hypothesis with probability (power) 0.80

with associated Type I error of 0.05. To account for loss to follow-up or incomplete data, we will enroll 30 subjects. Calculations performed using PS power and sample size program.¹²

Statistical analyses

The proposed strategy for statistical analyses of end-points is illustrated in Figure 2. All end-points will be analyzed by comparing change in outcome from study drug day 1 to study drug day 90. End-points will be summarized descriptively by treatment, and treatment effect will be compared using methods appropriate for a 2x2 crossover design. We do not anticipate substantial carry over effects by placebo or spironolactone on outcome measures due, in part, to the lengthy study drug wash out period.

[figure not shown]

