Appendix F

Cardiopulmonary Exercise Test with Innocor™

Exercise Protocol: Patients complete a trial of incremental exercise to a symptom-limited maximum. The tests are performed with the subject breathing room-air. Two minutes of rest are followed by 2 min of unloaded cycling/step protocol at 40-60 RPM. Work rate is continuously increased using a ramp protocol at 10, 15, 20 or 25 W/min. Ventilation, pulmonary gas exchange, heart rate (HR), and BP are measured continuously. A 12-lead EKG is obtained at rest and each minute of exercise.

Hemodynamic Measurements: Innocor™ gives the complete metabolic and hemodynamic profile comprising a conventional cardiopulmonary exercise test (CPET) together with non-invasive measurement of cardiac output. This unique combination enables the possibility to distinguish between ventilatory, central circulatory or peripheral causes of exercise intolerance.

By using inert gas rebreathing for the hemodynamic measurements the hazards and costs of using PA-catheters are eliminated and inaccuracies of other non-invasive methods avoided.

During a rebreathing test the subject rebreathes an oxygen enriched mixture containing very small amounts of two physiologically inert gases - one blood soluble and one insoluble component - from a closed rebreathing system. The test lasts about 5 breaths or 15 seconds. During this time the blood soluble gas is dissolved in the blood perfusing the ventilated parts of the lungs. Innocor™ measures the concentration curve of the blood soluble gas and calculates the wash-out rate, which is proportional to the Cardiac Output. Cardiac output will be measured at "Rest" and then at "Peak" exercise. In patients with a significant intra-pulmonary shunt, the shunt flow is calculated by using the well proven Fick principle for oxygen. The blood insoluble gas is measured to determine the lung volume and to account for other factors that affect the distribution of the blood soluble gas.

Physiologic Measurements: All exercise tests are performed at the BWH Cardiopulmonary Exercise Laboratory under the supervision of [name]., using an upright cycle ergometer/step protocol. Innocor™ will be utilized to obtain metabolic and spirometric data.

The following parameters will be obtained during the CPET:

Hemodynamic	Derived Hemodynamic	Metabolic	Spirometric
CO = Cardiac Output	SvO2 = Mixed venous oxygen saturation	VO2 = Oxygen uptake	FEV1 = Forced expiratory volume in 1 second

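### Section VI sets out to separate diuresis from a pulmonary vascular effect, but no stated analysis removes drug-related weight change from peak VO2, a primary end-point expressed per kg (a modest interpretation issue)

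*Combined protocol and SAP*

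**What the plan says.** Section VI, under the heading on assessing volume status, describes spironolactone's natriuretic effect as weak. It nevertheless provides for weight, jugular venous pressure and diuretic records "to assess the potential effect of spironolactone on outcome in PAH due to diuresis rather than change in pulmonary vascular function". Two uses of these records are given: to "analyze outcome results according to diuretic status", and to describe when and how far the drug affects plasma volume. Diuretic status is not defined.

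Specific Aim 1 gives peak VO2 in mL/kg/min, and Section VI makes it one of two primary end-points, with 6-minute walk distance (6MWD). The sample size uses the same scale: "If the true difference in mean response of matched pairs is 1.0 ± 1.7 mL/kg/min, we will need 25 subjects".

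The analysis text reads: "All end-points will be analyzed by comparing change in outcome from study drug day 1 to study drug day 90". The caption of the analysis figure describes a two-sided paired t test of the change on spironolactone against the change on placebo. Neither contains a weight term, an absolute VO2 analysis or a fixed-weight denominator. The figure itself is not shown in the text available for this review.

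The data needed are already collected. Appendix F lists "VO2 = Oxygen uptake" as well as the per-kg value among the exercise-test outputs. Section V lists a weight at Day 1 and Day 90 of each phase, and also says: "Weight will be obtained at home every day during participation in the study".

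**The concern.** Fluid loss on spironolactone shrinks the denominator of a per-kg end-point. Peak VO2 then rises with no change in oxygen uptake, and the rise favors spironolactone. The crossover does not cancel it: loss caused by the drug belongs to the spironolactone phase and goes straight into the treatment contrast.

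The named safeguard does not reach this. If diuretic status means use of loop or thiazide diuretics, the analysis compares groups of patients. Within each group, the per-kg value still carries whatever weight change the study drug caused. Describing the plasma-volume effect also leaves the end-point as it was.

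What is at stake is how a positive result is read. The Aim 1 hypothesis attributes better fitness to pulmonary vascular improvement. Part of a gain in mL/kg/min could be weight loss, and the planned outputs would not show how much.

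**Working it through.** **1. The plan's own figure.** Inputs from Section VI: difference 1.0, SD of paired differences 1.7, two-sided alpha 0.05, power 0.80. The noncentral t calculation for a paired t test gives power 0.788 at n = 24 and 0.806 at n = 25. The stated 25 is reproduced. Enrolling 30 allows for 1 - 25/30 = 16.7% loss.

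**2. Shift from weight alone.** Let p be baseline peak VO2 (mL/kg/min), W body weight (kg), and d the extra weight lost on spironolactone compared with placebo (kg). Hold absolute oxygen uptake at p × W and divide by test-day weight:

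shift = p × W/(W - d) - p = p × d/(W - d)

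The documents give none of p, W or d, and do not say which weight enters VO2/kg. Assumptions: p 10-16, W 60-90, test-day weight in the denominator. For d = 1 kg:

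| p | W | Calculation | Shift (mL/kg/min) | Share of planned 1.0 |
|---|---|---|---|---|
| 10 | 90 | 10/89 | 0.11 | 11% |
| 12 | 75 | 12/74 | 0.16 | 16% |
| 16 | 60 | 16/59 | 0.27 | 27% |

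At p = 12 and W = 75, a loss of 0.5 kg gives 6/74.5 = 0.08, and 2 kg gives 24/73 = 0.33. To produce the full 1.0 by weight alone, per-kg VO2 must go from 12 to 13, so weight must fall to 12 × 75/13 = 69.2 kg, a loss of about 5.8 kg.

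**3. Effect on the test.** Suppose oxygen uptake does not change at all. The two-sided rejection rate of the 5% paired t test (noncentral t, SD 1.7, n = 25) is then:

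| Shift | Rejection rate |
|---|---|
| 0 | 5.0% |
| 0.11 | 6.2% |
| 0.16 | 7.4% |
| 0.27 | 12.0% |

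With n = 30 and a shift of 0.16 it is about 8%.

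**4. Effect of a fixed denominator.** Dividing both the Day 1 and the Day 90 VO2 of a phase by that phase's Day 1 weight makes the shift in step 2 zero by construction. The scale stays in mL/kg/min, so the 1.0 benchmark still applies.

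**The case against.** The strongest reply is that the effect is probably small and the plan is not blind to it. Section VI expects weak natriuresis, and nothing in the documents supports a loss of 2 kg or more. 6MWD is not divided by weight. Nor are secondary end-points such as cardiac output, VE/VCO2 slope, pulmonary artery acceleration time and TAPSE, several of which bear directly on the proposed mechanism. A rise in peak VO2 caused only by a smaller denominator would not carry these with it. All of this stands and limits the point. It remains partial protection: the text does not say whether both primary end-points must be met, and agreement across other measures does not show how much of the peak VO2 estimate is weight.

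A second reply concerns the denominator. Weight is listed with the enrolling-site assessments, and the exercise test follows 24 to 72 hours later at the core facility. Test-day weight is plausible, but it is an assumption. This stands.

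A third reply is that an increase in VO2/kg is real on the end-point as defined, whatever its source. This also stands. A reader might infer from step 3 that the primary test has an inflated type I error. The documents do not support that, because the test is valid for the per-kg quantity. The 7.4% describes how often a pure weight effect would be declared a difference, which is a matter of mechanism.

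**Conclusion.** The point holds as a modest interpretation issue and a cheap improvement. The plan poses a question about diuresis, yet its one named analysis leaves drug-related weight change inside a primary end-point. The size is about 0.11 to 0.27 mL/kg/min per 1 kg of extra loss. That figure rests on assumed baseline values, test-day weight in VO2/kg and unchanged oxygen uptake. The amount of loss to expect is unknown, and the plan suggests it is small.

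Two stronger readings are tempting. One is that the plan offers no means at all of telling diuresis from a vascular effect; the end-points not divided by weight and the planned description of plasma volume contradict this. The other is that the sample size or the choice of end-point is wrong. The 25 reproduces, and weight alone would need about 5.8 kg of loss (at 12 mL/kg/min and 75 kg) to create the planned difference.

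**What to change.** Keep peak VO2 in mL/kg/min as a primary end-point. Add to Section VI one supportive analysis: the same treatment comparison, with each phase's Day 90 absolute VO2 divided by that phase's Day 1 weight. Absolute VO2 in mL/min is an acceptable alternative, though it loses the 1.0 benchmark. Report the estimate and 95% CI beside the primary result, together with the spironolactone-minus-placebo difference in Day 1 to Day 90 weight change. State which weight the exercise system uses for VO2/kg.

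State also that this removes only the body-weight denominator effect. Diuresis could change oxygen uptake itself, for example through right ventricular loading, so a gain that persists at fixed weight does not prove a vascular effect.

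Do not add a rule that turns on whether the fixed-weight result is significant. Take a total effect of 1.0 of which 0.84 is oxygen uptake (1 kg lost at 12 mL/kg/min and 75 kg), and treat the weight shift as constant across patients. Power at n = 25 is 0.806 for the per-kg result and 0.657 for the fixed-weight result. About (0.806 - 0.657)/0.806 = 18% of positive trials would then be called inseparable from diuresis although most of the effect is real. At 2 kg the figure is (0.806 - 0.474)/0.806 = 41%.

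The cost is one supportive analysis and one table, with no new visits, tests or patients and no alpha spent. The downsides are that it may weaken a positive peak VO2 claim, and that it also removes weight loss from causes other than diuresis, so it can understate a real gain in fitness per kg.

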Eligible participants will then be randomized to receive placebo or spironolactone (50 mg/d) for 90 days (Phase I). At the completion of Phase I, participants will undergo repeat end-point assessment followed by a 21-day drug wash out period. Then, the 90 day crossover phase of the trial will occur (Phase II), in which participants randomized to placebo in Phase I will be treated with spironolactone (50 mg/d) in Phase II and *vice versa*. At the conclusion of Phase II, end-point measures are reassessed.

Once all entry criteria have been met and random treatment assignment confirmed, the first dose of study drug 50 mg should be taken by the subject with or without food. Study drug should be taken once daily, preferably in the morning.

Spironolactone/placebo will be dispensed to patients at Brigham and Women's Hospital (BWH) at the time they are having the CPET-Innocor™ at Baseline, Phase 1 and Day 1, Phase II Visits. All drug containers will be returned to BWH at Day 90, Phase I and Day 90, Phase II Visits.

Study drug to be stored at room temperature.

Side effects of spironolactone include headache, diarrhea, cramps, drowsiness, rash, nausea, vomiting, irregular menstrual periods, and irregular hair growth. Fluid and electrolyte imbalance such as hyperkalemia may occur. Gynecomastia may also occur and is related to dose and duration of therapy. It usually reverses upon discontinuation of spironolactone.

VI. Biostatistical Analysis

Endpoints

Study Primary End-points: A two-primary end-point study model¹⁰ will be used in this study, to include change from baseline (study drug day 1) at study drug day 90 for each of the two trial phases in (i) 6 minute walk distance and (ii) peak VO₂ at the completion of exercise as a determinate of overall cardiopulmonary fitness.

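### Two primary endpoints with no stated rule for trial success: the 0.05 and 0.80 describe peak VO2 alone, not the trial's overall decision

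*Combined protocol and SAP*

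**What the plan says.** Specific Aim 1 (Section II) pairs the two outcomes: "i) 6 minute walk distance and (ii) peak oxygen consumption". Section VI, Endpoints, makes both primary, with peak VO2 as the second of the pair: "for each of the two trial phases in (i) 6 minute walk distance and (ii) peak". Statistical Methods repeats the model ("A two-primary end-point study model will be used in the proposed trial") and announces the details, but only a peak VO2 subsection follows. 6MWD has no matching one.

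For peak VO2, the plan prescribes a paired t test ("the treatment effect, will be compared using a 2-sided, paired") and sizes the trial on a paired difference of 1.0 with SD 1.7 mL/kg/min. It gives the number needed as follows: "we will need 25 subjects to be able to reject the null hypothesis with probability (power) 0.80". The error rate attached to that calculation is given once, there: "with associated Type I error of 0.05". Enrolment is then raised: "To account for loss to follow-up or incomplete data, we will enroll 30 subjects".

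Under Statistical analyses, "All end-points will be analyzed by comparing change in outcome from study drug day 1 to study drug day 90". The caption of the analysis schema applies the same two-sided paired t test to the end-points generally. No either/both rule, testing order, alpha split or multiplicity adjustment appears anywhere, and no assumed effect, SD, alpha or power is given for 6MWD.

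**The concern.** With two primary endpoints, Type I error and power for the trial depend on how the two results are combined, and the plan does not say how. There are two natural readings, and each has a different consequence.

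- **Either endpoint suffices.** Two tests at 0.05 give two chances of a false positive, so overall error exceeds 0.05.
- **Both are required.** Type I error is controlled without adjustment, but the chance of success is a joint power. The plan does not give it, and it cannot be higher than the power for peak VO2 alone.

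The practical problem is a split result, with one endpoint significant and the other not. The plan does not say whether that is success or failure. Deciding after the data are seen either accepts an inflated error rate or applies a standard the trial was not sized for. The gap cannot be credibly repaired after unblinding.

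**Working it through.** **Inputs from Section VI:** two primary endpoints; two-sided paired t test; for peak VO2, difference 1.0, SD 1.7, alpha 0.05, power 0.80, 25 evaluable, 30 enrolled.

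**Assumed, because the plan gives no values:** the correlation between the two test statistics (0 to 0.95), and either the 6MWD power or a 6MWD standardised effect equal to that for peak VO2 (1.0/1.7 = 0.588).

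**1. The plan's own figure.** Paired t power from the noncentral t distribution, df = n − 1, noncentrality = (1.0/1.7)√n:

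- n = 24: power 0.788
- n = 25: noncentrality 0.588 × 5 = 2.94, power 0.806
- n = 30: power 0.876

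So 25 is the smallest n reaching 0.80, and the arithmetic is right for peak VO2 alone.

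**2. Either endpoint suffices, no effect on either.** If independent, error = 1 − 0.95² = 0.0975. With correlation (bivariate normal, each test at two-sided 0.05):

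| Correlation | 0 | 0.5 | 0.8 | 0.9 | 0.95 |
|---|---|---|---|---|---|
| Overall Type I error | 0.0975 | 0.0907 | 0.0781 | 0.0704 | 0.0646 |

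The error tends to 0.05 only as the correlation approaches 1.

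**3. Both must win.** Joint power is at most the smaller of the two powers. If independent, with 6MWD power 0.80, it is 0.806 × 0.80 = 0.64. With correlation (bivariate normal):

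| Correlation | 0 | 0.5 | 0.8 | 0.9 |
|---|---|---|---|---|
| n = 25, 6MWD power 0.80 | 0.644 | 0.691 | 0.732 | 0.753 |
| n = 25, 6MWD power 0.95 | 0.765 | 0.784 | 0.800 | 0.804 |
| n = 30, both powers 0.876 | 0.767 | 0.796 | 0.824 | 0.839 |
| 6MWD power needed for joint 0.80, n = 25 | 0.993 | 0.983 | 0.951 | 0.917 |
| 6MWD power needed for joint 0.80, n = 30 | 0.914 | 0.882 | 0.840 | 0.820 |

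**4. How often the result is split (equal standardised effects).** If independent at n = 25: 2 × 0.806 × (1 − 0.806) = 0.313. Simulated paired t tests, 100,000 trials per setting:

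| Correlation | 0 | 0.5 | 0.8 | 0.9 |
|---|---|---|---|---|
| n = 25 | 0.313 | 0.228 | 0.144 | 0.101 |
| n = 30 | 0.219 | 0.163 | 0.105 | 0.075 |

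**5. Price of an alpha adjustment.** At two-sided 0.025, peak VO2 power is 0.707 at n = 25 and 0.799 at n = 30. This is the power Holm guarantees whatever happens on 6MWD. With equal standardised effects (simulated), Holm gives peak VO2 0.75 to 0.78 at n = 25 and 0.83 to 0.86 at n = 30.

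**The case against.** The strongest points on the other side are these.

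- **No passage says the tests are unadjusted.** This is true. It is read from silence, and 0.05 is never restated for 6MWD. But a plan that states no rule leaves the choice open, and that is the defect.
- **The direction of harm is undetermined.** This is also true. Error inflates only under an either-endpoint rule, and 9.75% is the zero-correlation case. Two measures of exercise capacity are plausibly correlated; at an assumed 0.5 to 0.8 the error is 9.1% to 7.8%, still well above 5%.
- **The cited precedent or the missing figure may hold the rule.** The figure's caption is printed and gives none. Reference 10, cited for the two-endpoint model, is in the printed list a study of physical activity in adults with congenital heart disease, so as printed it cannot supply one.
- **The joint-power and split-result figures rest on assumed 6MWD inputs.** They do, which is why they are ranges. The 0.0975 and the peak VO2 ceiling on joint power do not depend on them. The 0.0975 does take each test to have exactly 5% error. The preliminary carryover and period tests, and the additional 180-day peak VO2 comparison, could change that.
- **This is a 30-patient study and readers could apply Holm themselves.** The plan does not call itself a pilot. It states an efficacy hypothesis with a Type I error and a power, so the rule for declaring success belongs in it.

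**Conclusion.** The concern holds and should be fixed before unblinding. The sample size is arithmetically correct for peak VO2 (0.806 at 25 evaluable, 0.876 if all 30 are evaluable), but neither 0.05 nor 0.80 describes the trial's decision. Under an either-endpoint rule, overall error lies between 6.5% and 9.75% for correlations from 0.95 down to 0. Under a both-endpoint rule, error is controlled and joint power is capped at 0.806 (25 evaluable) or 0.876 (30). Whether it falls short of 0.80 cannot be known until 6MWD assumptions are stated. A split result would not be rare if the two standardised effects are equal: 10% to 31% of trials at 25 evaluable and 7% to 22% at 30, for correlations from 0.9 to 0. A different 6MWD effect would change those rates.

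**What to change.** Add one paragraph to Section VI that fixes a single rule holding overall error at two-sided 0.05. Any of these would do:

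1. **Fixed sequence.** Suggested text: *Peak VO2 is tested first at two-sided 0.05. 6MWD is tested at two-sided 0.05 only if peak VO2 is significant.* Peak VO2 is first here only because the trial is sized on it; the order is the sponsor's choice. Peak VO2 power stays at 0.806 with 25 evaluable. The cost is that 6MWD cannot be claimed if peak VO2 fails, so the chance of claiming 6MWD equals the joint power (0.65 to 0.76 at 25 evaluable, equal standardised effects assumed).
2. **Holm.** Suggested text: *The smaller p-value is compared with 0.025; if significant, the other is compared with 0.05.* No order is needed. The guaranteed peak VO2 power must be restated: it falls from 0.806 to 0.707 at 25 evaluable and from 0.876 to 0.799 at 30.
3. **Both must win.** Say so, and restate power as joint power under stated 6MWD assumptions. Holding joint power at 0.80 would probably need more patients, and I do not propose it. With independent endpoints and equal standardised effects, each endpoint needs power √0.80 = 0.894, which takes 32 evaluable; at the plan's ratio, 32/(25/30) = 38.4, so 39 enrolled.

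In every case, state that 0.80 refers to peak VO2 only, and add the assumed 6MWD effect, SD and resulting power. Options 1 and 2 need only wording and no extra patients. The 6MWD line takes somewhat more work, because the sponsor must find or justify a within-patient SD that the documents do not contain. The testing rule does not depend on it and should not wait for it.
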